⁵Austin PC, Stuart EA. (2017) The Performance of Inverse Probability of Treatment Weighting and Full Matching on the Propensity Score in the Presence of Model Misspecification When Estimating the Effect of Treatment on Survival Outcomes. Stat Methods Med Res, 26(4), 1654-1670

- 4. Evaluation of the balance of covariates: It will be carried out with graphical methods (QQ plots for continuous variables and bar graphs for nominal variables), and with descriptive numerical methods (standardized mean differences and variance ratios) and inferential methods (t tests and rank sum tests) ⁶.
- 5. Estimation of treatment effect: Treatment effects, according to the type of outcome, will be estimated using generalized linear models with weighting of the observations in the sample ⁷.
- 6. Sensitivity analysis: This analysis will be performed to determine the magnitude of the bias that may be produced by the omission of covariates. For this analysis, the methodology proposed by Carnegie, Harada, Dorie and Hill will be used ⁸.

In accordance with the specific objectives set out in the protocol, the following types of analysis are proposed:

- 1. For the objectives related to the comparison of time to hospitalization and time to death event between both cohorts, the respective incidence rates for each group and the survival functions will be calculated using Kaplan-Meier estimators.
 Comparisons between the survival functions of each of the two groups will be made with log- rank, Tarone-Ware or Peto-Peto Prentice tests, depending on the censoring pattern. Additionally, Cox models will be used to estimate the strength of association between type of treatment and time to event using the HRs metric.
 In these models, weighted samples will be used with the IPTW method and a group of time-dependent covariates will be incorporated (serum albumin, PEW, MIS, hs CRP, type of dialyzer).
- 2. To meet the objectives related to counting variables (days of hospitalization and non-fatal cardiovascular events), Poisson regression models or negative binomial

⁶Austin P.C. (2009) Balance diagnostics for comparing the distribution of baseline covariates between treatment groups in propensity-score matched samples. Stat Med 10;28(25):3083-107

⁷Austin P.C. (2016) Variance Estimation When Using Inverse Probability of Treatment Weighting (IPTW) With Survival Analysis. Stat Med. 35 (30), 5642-5655

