⁸Carnegie, N.B., Harada, M., Dorie, V., & Hill, J. (2016). treatSens: Sensitivity analysis for causal inference. Retrieved from https://cran.r-project.org/web/packages/treatSens/index.html

regression models will be used in case of overdispersion in the outcome variable. Within these models, the covariates that will be candidates for inclusion in the models are:

- a. For the outcome days of hospitalization: Serum albumin, PEW, MIS, hs CRP, dialyzer type
- 3. For non-fatal cardiovascular events outcome: Serum albumin, PEW, MIS, hs CRP, dialyzer type
- 4. For the objective related to the estimation of the association between serum albumin levels and the outcomes of mortality, non-fatal cardiovascular events, hospitalization events and days of hospital stay, the use of linear mixed models for longitudinal data is proposed. This strategy allows modeling the association between repeated measurements of independent variables and the proposed outcomes, in the presence of other variables that also vary over time. These models involve the combination of fixed effects and random effects models, and allow the inclusion of variables that change over time. To identify potential confounding variables, a directed acyclic causal diagram (DAG) will be performed. Additionally, G methods will be used for longitudinal data, which allow estimating the causal effect of an exposure that varies over time (in this case albumin levels) in the presence of confounding variables that also vary over time (hs CRP, MIS, PEW, FRR, type of dialyzer) that are in turn affected by the exposure. These methods may be more robust than traditional regression-based methods. The parametric G- formula and the weighted inverse probability of treatment estimation with marginal structural models 9will be used 10.11

⁹James M. Robins, Sander Greenland, Fu-Chang Hu. Estimation of the Causal Effect of a Time-Varying Exposure on the Marginal Mean of a Repeated Binary Outcome, J Am Stat Assoc. 1999; 94:447, 687-700.

¹⁰Miguel A Hernán, Babette Brumback, James M Robins. Marginal Structural Models to Estimate the Joint Causal Effect of Nonrandomized Treatments. J Am Stat Assoc. 2001; 96:454, 440-448.

¹¹Sally Picciotto, Miguel A. Hernán, John H. Page, Jessica G. Young, James M. Robins. Structural Nested Cumulative Failure Time Models to Estimate the Effects of Interventions. J Am Stat Assoc. 2012;107:499, 886-900.

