PEW	Mean (SD),	Mean (SD),	Mean (SD), Median
	Median (IQR)	Median (IQR)	(IQR)
PEW categorized			
0=No wear (0-2)	n(%)	n(%)	n(%)
1=With wear (>=3)	n(%)	n(%)	n(%)
Malnutrition-			
Inflammation Scale			
Hydration status			
0= No signs and	n/ 9/)	n/ 9/)	n/ 0/)
symptoms	n(%)	n(%)	n(%)
1=Edema below the	n/ 9/)	n/ 9/)	n/ 0/)
knees	n(%)	n(%)	n(%)
2=Edema above knees	n(%)	n(%)	n(%)

Karnofsky	Mean (SD),	Mean (SD),	Mean (SD), Median
	Median (IQR)	Median (IQR)	(IQR)
Nutritional assessment			
1	n(%)	n(%)	n(%)
2	n(%)	n(%)	n(%)
3	n(%)	n(%)	n(%)

^{*}Variables measured every 6 months

Table 7Hospitalization variables

Variable	HDx	HF-HD	HF-HD
Hospitalization yes	n(%)	n(%)	n(%)
or no	11(70)	11(70)	11(70)
Diagnosis in			
hospitalization			
1=Cat 1	n(%)	n(%)	n(%)
2=Cat2	n(%)	n(%)	n(%)
3=Cat3	n(%)	n(%)	n(%)
Major			
cardiovascular	n(%)	n(%)	n(%)
event yes or no			
Fatal cardiovascular	n(%)	n/ 0/)	n(%)
event yes or no	11(70)	n(%)	11(70)
COVID in	n(%)	n(%)	n(%)
hospitalization	11(70)	11(/0)	11(70)
Days of hospital	Mean (SD), Median	Mean (SD), Median	Mean (SD), Median
stay	(IQR)	(IQR)	(IQR)

Table 8Mortality variables*

	HDx	HF-HD	Total
Death yes or no	n(%)	n(%)	n(%)
Cause of death			
1=Cancer	n(%)	n(%)	n(%)
2= Cardiovascular	n(%)	n(%)	n(%)
3=Infectious	n(%)	n(%)	n(%)
4=Metabolic	n(%)	n(%)	n(%)
5=Respiratory	n(%)	n(%)	n(%)
6 = COVID	n(%)	n(%)	n(%)

7=Other	n(%)	n(%)	n(%)
8= Unknown	n(%)	n(%)	n(%)
Dialysis-related death yes or no	n(%)	n(%)	n(%)

^{*}Variables measured every 6 months

Table 9End-of-follow-up variables*

	HDx	HF-HD	Total
Reason for			
termination of			
follow-up			
1= Death	n(%)	n(%)	n(%)
2= Loss of tracking	n(%)	n(%)	n(%)
3= Change of			
health	n(%)	n(%)	n(%)
provider/insurer			
4= Recover kidney	n(%)	n(%)	n(%)
function	11(70)		
5= Suspension of	n(%)	n(%)	n(%)
treatment			
6= Transplant	n(%)	n(%)	n(%)
7= Dialyzer change	n(%)	n(%)	n(%)
8= Changed to DP	n(%)	n(%)	n(%)
9= End of study	n(%)	n(%)	n(%)

^{*}Variables measured every 6 months

4. Data extraction and preparation

After the measurement of variables and the collection of data are completed, the sponsor of the study must provide the analysis group with a file containing the results of the measurements of the variables considered in the project. It is recommended that this file be in a plain text format, preferably as comma-separated text (*. csv) or tab-separated text (*. txt). Additionally, the sponsor is required to provide a file with the variable dictionary that must contain the following information:

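### The plan has no censoring weights, assumption or sensitivity analysis for the non-death exits in Table 9, so the albumin marginal structural model and the 4-year survival curves can be biased

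*SAP*

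**What the plan says.** All analysis text is in SAP section 3.1.2.2.

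- **Albumin effect (analysis item 4).** Besides linear mixed models, two G methods are planned: the parametric G-formula and "the weighted inverse probability of treatment estimation with marginal structural models". The item names hs CRP, MIS, PEW, FRR and type of dialyzer as time-varying confounders that albumin itself affects.
- **Time to death and to hospitalization (analysis item 1).** Kaplan-Meier estimators are compared with one of three log-rank-type tests, chosen "depending on the censoring pattern". Cox models follow: "In these models, weighted samples will be used with the IPTW method and a group of time-dependent covariates will be incorporated". The listed covariates are albumin, PEW, MIS, hs CRP and type of dialyzer.
- **Sensitivity analysis (step 6).** "This analysis will be performed to determine the magnitude of the bias that may be produced by the omission of covariates".
- **Missing data (section 3.1.5).** The missingness mechanism is assessed and an imputation procedure chosen. Ending of follow-up is not mentioned.
- **Exits (section 3.2.1, Table 9).** The reasons for ending follow-up include "2= Loss of tracking" and "8= Changed to DP". They also include change of provider or insurer (3), recovery of kidney function (4), suspension of treatment (5), transplant (6) and dialyzer change (7). The table is descriptive, and no analysis uses the codes.

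Mortality and 4-year survival are primary outcomes (section 2.4).

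**The concern.** Treatment weights make exposure groups comparable on measured confounders. They do nothing about who stays under observation. A marginal structural model deliberately leaves the time-varying confounders out of its outcome model. If those same variables influence leaving, conditioning on the outcome-model terms does not make censoring independent, and the usual remedy is a second set of weights for remaining in follow-up. Kaplan-Meier curves and log-rank-type tests are more exposed still, because they need leaving to be unrelated to prognosis within each cohort.

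At stake are the albumin effect (general objective and specific objective 6) and the 4-year survival estimates. The two planned albumin estimates could also disagree for this reason alone: a G-formula can account for leaving that depends on the modelled history, whereas a model with treatment weights only does not.

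**Working it through.** The SAP has no figure on this point to reproduce. Its only computed figure, the 90% power in the sample size section, does not bear on it.

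**1. Does any passage cover leaving?** Three come close, and none does.
- The censoring pattern is used only to choose among tests. Each of those tests still assumes uninformative censoring.
- The sensitivity analysis concerns omitted covariates.
- The missing-data text concerns imputing variables.

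The sentence on weights refers to the models, so the SAP does not say whether the survival curves are weighted at all.

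**2. Kaplan-Meier.** All inputs except the 4-year horizon are assumptions:
- risk marker z, standard normal;
- death hazard λ(z) = 0.12·exp(0.7z) per year, i.e. doubling per SD;
- exit hazard ε(z) = η·exp(dz), with η from 0.05 to 0.15 and d = 0.7 (sicker patients leave), 0 (unrelated) or −0.7 (healthier patients leave).

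True 4-year survival is E[exp(−4λ)] = 59.0%. In large samples Kaplan-Meier tends to exp(−∫₀⁴ h(t)dt), where h(t) = E[λ·exp(−(λ+ε)t)] / E[exp(−(λ+ε)t)]. Numerical integration gives:

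| η per year | Sicker leave: KM (error); left by year 4 | Healthier leave: KM (error); left by year 4 |
|---|---|---|
| 0.05 | 60.4% (+1.4 points); 15% | 57.6% (−1.4 points); 18% |
| 0.10 | 61.7% (+2.7 points); 27% | 56.3% (−2.7 points); 30% |
| 0.15 | 62.8% (+3.8 points); 36% | 55.1% (−3.8 points); 40% |

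With d = 0 the error is zero. Simulations of the same set-up put the upper end at 3.7 to 3.9 points. These errors apply to one cohort's curve. If both cohorts lose patients in the same way, much of the error cancels in their difference.

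**3. Albumin marginal structural model.** This was simulated over eight six-month intervals with weighted pooled logistic regression (six runs of 150,000 patients). All parameters are assumed. The Monte Carlo SE of a log hazard ratio is about 0.02.

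| Leaving | Share leaving | Treatment weights only | Plus censoring weights |
|---|---|---|---|
| None | 0% | 0.634 | 0.634 |
| Random | 39% | 0.639 | 0.639 |
| Depends strongly on inflammation | 28% | 0.635 | 0.630 |
| Depends on inflammation, differently by albumin level | 33% | 0.688 | 0.645 |

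Only the last row moves: ln(0.688/0.634) = 0.082, against a combined Monte Carlo SE of √(0.017² + 0.022²) = 0.028. The log hazard ratio shrinks from −0.456 to −0.374, about 18%. A separate simulation under other assumptions moved an albumin odds ratio only from 0.67 to 0.68–0.69.

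**4. Cox model for the dialyzer.** In the simulation of step 3, the model as the SAP writes it (IPTW plus time-dependent covariates) stays at 0.900 to 0.906 in all four rows. A dialyzer model with IPTW but no time-dependent covariates moves from 0.666 to 0.714 (third row) or 0.703 (fourth row). Censoring weights return it to 0.667 and 0.675. The gap between 0.90 and 0.666 comes from adjusting for post-baseline variables. It is a separate issue that censoring weights would not cure.

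**The case against.** **The Cox models.** A reader might infer that they rest on treatment weights only and are biased too. The text does not support that. Cox regression needs censoring to be independent given its covariates, and albumin, PEW, MIS and hs CRP are all in the model as time-dependent terms. Null hazard ratios of 0.96, 0.93 or 0.86 can be produced from assumed exits, but only in a single-covariate Cox model that the SAP does not plan. The 0.86 also needs the two cohorts to lose opposite kinds of patients. With the risk marker in the model the ratios are 0.99 to 1.02. This objection stands for exits driven by the listed covariates. It does not reach exits driven by FRR, which the SAP itself calls a time-varying confounder but omits from the Cox list, or by insurer or admissions.

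**Certainty.** A reader might also infer that bias is established. It is not. The SAP gives no exit rates and nothing linking exit to prognosis, and two of the three exit scenarios for the albumin model showed no visible shift.

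**Silence.** The SAP does not say that treatment weights are the only weights, nor in words that patients are censored at the Table 9 codes; the latter is inferred from the table. The plan also pairs the methods: "The parametric G- formula and the weighted inverse probability of treatment estimation" are both intended, and the G-formula can handle leaving that depends on modelled history. That is fair, but the SAP does not say how the G-formula will treat leaving. Where a plan specifies its weights, those for remaining in follow-up belong beside them.

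**Conclusion.** The concern holds in a conditional form. The SAP names treatment weights only for the albumin marginal structural model and plans Kaplan-Meier curves with log-rank-type tests, with nothing stated for the seven non-death exits. If hs CRP, MIS, PEW, FRR or similar factors also drive leaving, the albumin effect and the 4-year survival estimates can be biased.

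The size cannot be known from the document. Under the assumed exits of 5 to 15% per year tied to risk, a cohort's 4-year survival is off by about 1.4 to 3.8 points, upwards if sicker patients leave and downwards if healthier ones do. The albumin estimate shifts little or modestly, and noticeably only when the link between inflammation and leaving differs by albumin level. The Cox models are exposed only to exits driven by factors outside their covariate list. The change is worth making before analysis, since it is cheap and mostly uses variables already in the plan.

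**What to change.** 1. For each non-death code in Table 9 (2 to 8), state whether it is censoring or a competing event for each outcome. Reconcile code 7, where a dialyzer change ends follow-up, with the listing of dialyzer type as a time-dependent covariate in the Cox models.
2. For codes treated as censoring, estimate stabilised inverse-probability-of-censoring weights by pooled logistic regression per six-month interval. Use dialyzer, the baseline propensity covariates, insurer, and the latest albumin, hs CRP, MIS, PEW, urine output and admissions. Truncate at percentiles fixed in advance.
3. Multiply these with the treatment weights in the albumin marginal structural model. Apply them to the survival curves as well, and say that the curves are weighted.
4. Repeat the Cox models with these weights as a sensitivity analysis.
5. Define the G-formula contrast under the same exit rule.
6. Table 9 already reports exits by code and cohort; add a breakdown by albumin level.

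The cost is SAP wording, more analysis work and somewhat wider intervals; how much wider with 1098 patients has not been calculated. There are two limits. The weights correct only for measured drivers of leaving. The SAP tables show urine output only under medical history (Table 2), so whether repeated values exist should be confirmed.

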3.1.5. Handling missing data

Considering that in the present study data from a standardized clinical registry of proven quality in previous research will be used, a low amount of missing data is expected in the study variables. However, it is noted that the amount or pattern of missing data may affect the quality of the statistical estimates. Missing data and the mechanism by which they occur will be evaluated: MCAR (Missing Data). completely at random), MAR (Missing at random) and MNAR (Missing not at random), according to this evaluation, the appropriate data imputation procedures will be defined for each case

3.1.5 . Sample size:

Based on the availability of the assembled cohorts of 1098 patients, 564 on MCO in the Theranova® dialyzer cohort and 534 on conventional HD in the AF dialyzer cohort. This provides 90% power considering an IRR 0.82 for all-cause hospitalization and a significance level of 0.05 (26).

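### The 90% power is stated for a hospitalization rate ratio, but the analysis assigned to hospitalization is a Cox/log-rank comparison that reaches 90% only if about 97% of patients are hospitalized

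*SAP*

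**What the plan says.** Section 3.1.5 (Sample size) starts from existing cohorts: "Based on the availability of the assembled cohorts of 1098 patients", split as "564 on MCO in the Theranova® dialyzer cohort and 534 on conventional HD in the AF dialyzer cohort". It then states: "This provides 90% power considering an IRR 0.82 for all-cause hospitalization and a significance level of 0.05". It cites a reference (26), but names no test, sidedness, baseline rate, follow-up time, dispersion or allowance for weighting.

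Section 2.4 lists hospitalization events per patient-year as the first primary outcome. That is a rate, to which an IRR is suited.

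Section 3.1.2.2 then sets out the analyses by objective:

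- **Item 1, time to hospitalization and time to death:** incidence rates by group, Kaplan-Meier curves, log-rank type tests, and Cox models giving hazard ratios. For these models "weighted samples will be used with the IPTW method".
- **Item 2, count outcomes:** Poisson models, or else negative binomial, which as "regression models will be used in case of overdispersion in the outcome variable". The outcomes named are days of hospitalization and non-fatal cardiovascular events. The number of hospitalizations is not among them.

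Section 3.1.1 likewise describes the hospitalization outcome as a time from cohort entry.

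**The concern.** The power statement and the analysis plan describe two different comparisons of the same outcome. A rate comparison uses every admission; a first-event comparison uses at most one per patient. The same 1,098 patients can therefore give very different power for a ratio of 0.82, and a figure that is right for one need not hold for the other.

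What is at stake is how a null result is read. If the Cox model shows no clear difference, the SAP as written invites the reader to set that result against 90% power and take it as strong evidence against an 18% reduction. The test that was run may have had appreciably less.

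**Working it through.** **Inputs from the SAP:** n₁ = 564 (MCO), n₀ = 534 (high flux), ratio 0.82, significance level 0.05, power 90%. **Assumed:** a two-sided test (one-sided also shown), and time to hospitalization meaning first hospitalization.

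**The stated 90%.** It can be neither reproduced nor refuted from the SAP, because a rate test also needs the mean number of admissions per patient and the dispersion. The two possible analyses are therefore checked in turn.

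**Step 1. Cox/log-rank, as assigned to hospitalization.** Events needed (Schoenfeld): (1.960 + 1.282)² / [ln(0.82)² × p(1 − p)], with p = 564/1098 = 0.5137.

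= 10.507 / (0.03938 × 0.2498) ≈ 1,068, and 1,068/1,098 = 97.3%.

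Freedman's formula gives 1,075 (97.9%). One-sided, Schoenfeld gives 871 (79.3%).

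Power = Φ(√(events × 0.2498) × 0.1985 − z), with z = 1.960 two-sided and 1.645 one-sided:

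| Patients hospitalized | Two-sided | One-sided |
|---|---|---|
| 50% | 64% | 75% |
| 60% | 72% | 82% |
| 70% | 79% | 87% |
| 80% | 84% | 90% |
| 90% | 88% | 93% |
| 100% | 91% | 95% |

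These figures are before weighting. If IPTW inflated the variance by 1.25 (an assumption), two-sided power with every patient hospitalized would equal that for 1,098/1.25 = 878 events, or 84%.

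**Step 2. Rate comparison, to which an IRR belongs.** Let m be the mean admissions per high-flux patient over follow-up and k the negative binomial dispersion (k = 0 is Poisson). Then

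Var(log IRR) = (1/(0.82m) + k)/564 + (1/m + k)/534.

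For 90% power, two-sided, this must not exceed 0.03938/10.507 = 0.003748.

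- Poisson: (1/(564 × 0.82) + 1/534)/m = 0.003748 gives m = 1.08.
- Dispersion adds k(1/564 + 1/534) = 0.003646k. The m needed becomes 1.42 at k = 0.25, 2.10 at k = 0.5, 3.98 at k = 0.75 and 39 at k = 1.
- Above k = 0.003748/0.003646 = 1.03, no length of follow-up reaches 90%.

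Power over assumed values (none is given in the SAP):

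| m | k = 0 | k = 0.25 | k = 0.5 | k = 1 | k = 1.5 |
|---|---|---|---|---|---|
| 1 | 88% | 81% | 74% | 62% | 53% |
| 2 | 99% | 96% | 89% | 75% | 63% |
| 3 | 100% | 99% | 94% | 80% | 67% |
| 4 | 100% | 100% | 96% | 83% | 69% |

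**Step 3. The two analyses under one scenario.** Take Poisson counts with m = 1.07, close to where the rate test has 90% power. The share with at least one admission is then 1 − e^(−1.07) = 66% in high flux and 1 − e^(−0.877) = 58% in MCO, or 62% overall. The first-event test at a hazard ratio of 0.82 then has power of about 0.735. A figure that is correct for the rate test would thus be well off for the Cox test.

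**The case against.** The strongest reply is that the power sentence names an IRR and the primary outcome is a rate, so the 97% arises only by recasting that IRR as a first-event hazard ratio. The SAP never uses the word first, and does not state sidedness; one-sided, 79% hospitalized would do. Item 1 also computes incidence rates, and step 5 of the propensity score procedure provides for weighted generalized linear models according to outcome type. All this is fair. It shows that a rate analysis may have been intended. It does not show that one was specified: the rates in item 1 are calculated, but the tests and models there are time-to-event, and step 5 is generic.

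A reader might go further and infer that the 90% is simply wrong, or that a rate analysis would fail under ordinary overdispersion. The SAP does not support that. It gives no rate, follow-up or dispersion, and with 2 to 4 admissions per patient and k of 0.25 to 0.5 the unweighted power is 89% to over 99%. The SAP's remark on overdispersion belongs to hospital days and cardiovascular events, not to admissions. Nor must weighting cost power: the data preparation step deliberately adds covariates related only to the outcome, on the ground that this can raise it.

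The missing inputs may stand in the protocol or the cited reference, so their absence from this section is not in itself the defect. Powering on one of several primary outcomes, and not on albumin, is not an error either. Finally, the planned 95% confidence intervals would show the precision of a null result; that limits the harm but does not make the power sentence match the analysis.

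**Conclusion.** The point holds as an internal mismatch. The SAP attaches 90% power to a rate ratio, while the only analysis it specifically assigns to hospitalization yields a hazard ratio, and no count model is explicitly assigned to the primary per-patient-year outcome. Under the first-event, two-sided reading, the specified test has 64% to 84% power if 50% to 80% of patients are hospitalized. It reaches 90% only at about 97%, and no more than 91% if all are. The end-of-follow-up table lists transplant, change of insurer, dialyzer change and other exits, so near-universal hospitalization should not be presumed.

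For a rate test the 90% remains open: attainable with Poisson counts at about 1.08 admissions per high-flux patient or with modest overdispersion and more admissions, and out of reach for k above about 1.03. It would be wrong to read this point as showing that the figure is false for that test.

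**What to change.** 1. In section 3.1.2.2, item 2, add hospitalization events to the outcomes analysed by count models. Specify an IPTW-weighted negative binomial (or Poisson) model with log person-time as offset and robust variance. Name it as the analysis to which the IRR and the power refer, and keep the Cox model as supportive.
2. In section 3.1.5 (Sample size), restate the power for that model, with sidedness, from the assembled cohort's high-flux rate, follow-up and dispersion and the weighting design effect, over a range of values. Alternatively, replace the 90% by the detectable IRR or the expected 95% confidence interval width.
3. Do not apply the 90% to the Cox analysis.

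The cost is SAP wording and a short calculation on data already assembled. The stated power may become less favourable. No extra patients are needed.
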